important results, as also witnessed by the approval of five ICIs by the United States Food and Drug Administration (FDA) in the last few years: the PD-1 inhibitors, pembrolizumab and nivolumab, and the PD-L1 inhibitors atezolizumab, avelumab, and durvalumab [15,16]. However, only a small subset of advanced-stage UC patients may benefit from immunotherapy reaching a durable response. Antibodies–drug conjugates such as enfortumab vedotin, directed against nectin-4, and sacituzumab govitecan, directed against Trop-2, have been compared with standard chemotherapy in two randomized clinical trials including patients with locally advanced or mUC who had previously received platinum-based treatment and subsequently PD-1 or PD-L1 inhibitor. Both drugs shown to significantly improve survival compared to chemotherapy [17,18]. This led to the FDA approval of enfortumab vedotin for advanced-stage UC patients who had previously received PD-1 or PD-L1 inhibitor and platinum-containing chemotherapy, or who are ineligible for cisplatin-containing chemotherapy and had previously received one or more lines of systemic therapy [17,19].

With the emerging therapeutic options available, there is an urgent need for the identification of predictive biomarkers of response to ICIs, as well as a deeper understanding the role of immunotherapeutic agents in mUC [20]. Recently, several emerging studies aimed to evaluate biomarkers and predictors of response in this setting, including protein markers, immune-related cells, genetic markers, and host-related factors [21–22]. Regarding the latter, only a few studies

have investigated the putative predictive value of routinely assessed clinico-pathological data, including age, gender, liver metastases, and histological features.

The ARON-2 Study has been designed to share and analyze the global real world experiences with the use of pembrolizumab as first and second line and enfortumab vedotin for mUC aimed to analyze the efficacy and safety of these therapeutic approaches in specific subpopulations and to investigate for the presence of prognostic factors in this context.

2. Study Design and Endpoints

The ARON-2 Study is designed as an International Multicentric Retrospective Study to collect global experiences with the use of pembrolizumab and enfortumab vedotin used in different settings in patients with metastatic UC (mUC).

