2.1 Primary End-Point

- To analyze real-world data on the efficacy and safety of pembrolizumab and enfortumab vedotin in patients with mUC.

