2.2 Secondary End-Points

- To apply artificial intelligence technology to the study of real-world data for clustering and Artificial Neural Network analyses

The ARON PROJECT

Global experiences, perspectives and access to cure in patients with genitourinary tumors

- To assess the prognostic role of smoking attitude, obesity, age, renal insufficiency, primary tumor location, histology and concomitant medication in patients treated with pembrolizumab and/or enfortumab vedotin
- To compare different therapeutic sequences in mUC patients

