2.3 Evaluation of the Endpoints

- Overall Survival (OS) will be defined as a time from the start of the therapy until death from any cause
- Progression-Free Survival (PFS) will be defined as a time from the start of the therapy until progression or death from any cause. Patients switched to the following line of treatment without progression or lost at follow-up at the time of analysis were censored at their last follow-up date
- Radiological assessment was performed according to the RECIST 1.1 criteria [23] and the data on objective response (complete regression=CR, partial regression=PR, stable disease=SD or progressive disease=PD) will be collected and analyzed
- The Overall Response Rate (ORR) and Disease Control Rate (DCR) will be defined as the rates of CR + PR and CR + PR + SD, respectively (according to the RECIST 1.1 criteria) [23]
- Treatment related adverse events (e.g., cutaneous toxicity, neurological toxicity and hyperglycemia/mellitus diabetes) will be assessed according to

The ARON PROJECT

Global experiences, perspectives and access to cure in patients with genitourinary tumors

the Common Terminology Criteria for Adverse Events (CTCAE) v 5.0 [24].

Grade ≥ 3 adverse events will be analyzed with a special focus

3. Study Population

The ARON-2 study retrospectively analyze patients treated with pembrolizumab, as first-line therapy in platinum-unfit patients or as second-line therapy in patients progressed after previous platinum-based chemotherapy, and/or enfortumab vedotin, as third-line therapy in patients previously treated with platinum-based chemotherapy and subsequently with PD-1 or PD-L1 inhibitor.

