3.3 Estimated Enrollment

In order to determine the minimum sample size for the purpose of the analysis on patients treated by pembrolizumab, we identified the smallest subpopulation among the planned sub-analyses, which was represented by obese patients with advanced UC. According to the literature, the incidence of obesity can be estimated at 30% in patients with UC [21]. In the study that led to the FDA approval of Pembrolizumab in UC patients [15], the median OS in the standard control arm with chemotherapy was 7.4 months, with a hazard ratio of 0.73. In our study, we set a significance level of 0.05 and the power to 80% for a minimal observation time of 12 months [22,25]. Under these conditions, we estimated an enrollment of 110 obese UC patients, in order to expect to observe at least 78 events in this group, which corresponds to an estimated overall study population of 367 patients affected by advanced UC.

In the study that led to the FDA approval of enfortumab vedotin in UC patients [17], the estimated percentage of patients alive at 12 months was 51.5% (95% CI, 44.6 to 58.0) in the enfortumab vedotin group and 39.2% (95% CI, 32.6 to 45.6) in the chemotherapy group with a delta of 12.3 among the two groups. In this study,

The ARON PROJECT

Global experiences, perspectives and access to cure in patients with genitourinary tumors

we tested the hypothesis that, using the enfortumab vedotin in clinical practice, OS would reach at least 60% after 12 months from the start of therapy. Study plan will include at least 361 patients with an estimated drop out of 10–15%. It was calculated that a minimum of 311 evaluable patients should be enrolled with an α of 0.05 and a β of 0.80 (STATASOFT).

4. Statistical Analysis and Data Collection

PFS and OS will be estimated by Kaplan-Meier method with Rothman's 95% confidence intervals (CI) and compared by using the log-rank test. Univariate and multivariate analyses will be performed by using Cox proportional hazards models. The chi-square test will be used to compare categorical end-points. Significance levels will be set at a 0.05 value and all p values will be two-sided. The statistical analysis will be performed using MedCalc version 19.6.4 (MedCalc Software, [name]).

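### For comparing ORR, DCR and adverse events between non-randomised groups, the protocol names only an unadjusted chi-square test, while multivariable adjustment is confined to Cox models

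*Protocol*

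**What the plan says.** Section 2 describes the design: "The ARON-2 Study is designed as an International Multicentric Retrospective Study". The primary end-point (section 2.1) is "To analyze real-world data on the efficacy and safety of pembrolizumab and enfortumab vedotin in patients with mUC"; it states no contrast between groups.

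The comparisons are among the secondary end-points (section 2.2): "To assess the prognostic role of smoking attitude, obesity, age, renal insufficiency, primary tumor location, histology and concomitant medication" and "To compare different therapeutic sequences in mUC patients".

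The categorical efficacy end-points are in section 2.3: "The Overall Response Rate (ORR) and Disease Control Rate (DCR) will be defined as the rates of CR + PR and CR + PR + SD". The same section grades adverse events by CTCAE v5.0 with particular attention to grade 3 or higher. It gives no observation window and no exposure denominator.

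Section 4 assigns methods to outcome types. PFS and OS get Kaplan-Meier and log-rank. It adds "Univariate and multivariate analyses will be performed by using Cox proportional hazards models", and for the remaining outcomes "The chi-square test will be used to compare categorical end-points". All tests are two-sided at 0.05. No logistic model, stratified test, propensity method or exposure-adjusted rate is named.

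**The concern.** The protocol accepts that survival comparisons in this cohort need multivariable adjustment, yet the method it names for response and adverse events has none. No reason is given for treating them differently.

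The groups to be compared are not exchangeable. Section 3 ties line of therapy to the patient's condition and history: pembrolizumab first line for those unfit for platinum, pembrolizumab second line after platinum, and enfortumab vedotin third line. Age, renal insufficiency and concomitant medication can all travel with fitness and hence with line. Therapeutic sequences differ in line by construction.

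If the text is followed as written, a factor could be reported as linked to ORR when the link belongs to another baseline trait. For adverse events there is a second issue. A crude proportion depends on how long patients stayed on drug, and that can differ between groups with different prognosis.

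**Working it through.** **The plan's own figures.** The protocol gives no response rate, adverse-event rate or time on treatment, so there is no stated result to reproduce on this point. Only the group sizes come from the document. Section 3.3 gives 110 obese patients, 30% obesity and 367 in total: 110 / 0.30 = 366.7, rounded up to 367. The comparison group is 367 − 110 = 257. Everything else below is an assumption, shown as a range.

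**Response: method.** Suppose one binary baseline trait changes ORR from r0 (absent) to r1 (present), is present in a proportion q of a group, and the group itself has no effect. The crude group rate is

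p = q·r1 + (1 − q)·r0.

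The chance that a two-sided 5% chi-square rejects is, by the normal approximation,

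Φ((−1.96·SE0 − d)/SE1) + 1 − Φ((1.96·SE0 − d)/SE1),

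where d = p1 − p2, SE0 uses the pooled rate and SE1 the two separate rates.

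**Response: worked case.** Trait in 60% v 30%, ORR 30% without it and 15% with it:

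- p1 = 0.6 × 0.15 + 0.4 × 0.30 = 0.210
- p2 = 0.3 × 0.15 + 0.7 × 0.30 = 0.255
- d = −0.045; pooled rate 0.2415; SE0 = 0.0488; SE1 = 0.0474
- rejection = 0.143 + 0.0015 = 14.5%

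**Response: range.**

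| Trait prevalence (110 v 257) | ORR without / with trait | Crude ORR | Rejection at nominal 5% |
|---|---|---|---|
| 50% v 40% | 35% / 25% | 30.0% v 31.0% | 5.3% |
| 50% v 30% | 30% / 15% | 22.5% v 25.5% | 8.9% |
| 60% v 30% | 35% / 20% | 26.0% v 30.5% | 13.5% |
| 60% v 30% | 30% / 15% | 21.0% v 25.5% | 14.5% |
| 60% v 30% | 30% / 10% | 18.0% v 24.0% | 23.5% |

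Simulation of the 2×2 tables agrees: 8.9%, 14.5% and 24.0% for the second, fourth and fifth rows. A more extreme imbalance (70% v 30%, ORR 40% / 15%) reaches 48.5%. An analysis that adjusts correctly for the trait would return to about 5%.

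**Adverse events.** Take the same monthly hazard h in both groups and fixed time t on drug, so the proportion with an event is 1 − exp(−h·t). With h = 0.03 and 3 v 6 months:

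- 1 − exp(−0.09) = 8.6%
- 1 − exp(−0.18) = 16.5%

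Chi-square calls this significant in 51% of studies by the same approximation (52.5% by simulation). If time on drug is exponential with those means, the figure is 44%. At 3 v 4 months, with h = 0.03 to 0.05, it is 10% to 15% across both exposure models. These are false positives only if the question concerns the event rate per month on drug. As statements about the proportion of patients affected, the differences are real.

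**The case against.** **The primary end-point.** A reader might infer that a large part of the primary end-point goes unadjusted, since safety and response belong to it. The document does not support that. Section 2.1 states no comparison, a rate within one treated cohort needs no confounder adjustment, and the chi-square sentence applies only where end-points are compared. Efficacy also includes OS and PFS, which do have multivariable models. This objection stands, and it confines the point to the secondary comparisons.

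**Exclusivity.** The protocol does not say that chi-square is the sole analysis, and a statistical analysis plan that is not shown may add models. That is fair: it is the only method named, not the only one permitted. But section 4 does choose a method for these outcomes, and an analysis following it would be unadjusted.

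**Inferred contrasts.** Section 2.2 does not say that ORR or adverse events will be compared for each factor. This also stands. However, section 1 aims at efficacy and safety in specific subpopulations, and section 4 foresees comparing categorical end-points.

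**ORR v PFS.** Log-rank and univariate Cox results will also be unadjusted, so crude PFS can be set beside crude ORR. That softens any apparent conflict between the two but does not remove the confounding in ORR.

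**Direction for adverse events.** It is tempting to say that a group stopping early will always look safer. That fails if it stops because of toxicity. Crude incidence is also a legitimate quantity in its own right, and a constant-rate model brings assumptions of its own.

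**Conclusion.** The point holds for comparative analyses of ORR and DCR between the non-randomised groups of section 2.2, and in weaker form for grade 3 or higher adverse events. The named method does not address differences in prognosis or line of therapy, although the protocol plans multivariable models for survival.

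The size rests entirely on assumed imbalances; only the group sizes of 110 and 257 derive from the document. Under mild confounding the chi-square error rate stays at about 5%, and under strong confounding it rises to about 15% to 24%. It is therefore a risk that depends on the data, not a demonstrated error. Descriptive rates within the pembrolizumab and enfortumab vedotin cohorts are untouched. For adverse events the crude proportion is acceptable if read as such; what is missing is a companion measure that accounts for time on treatment.

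**What to change.** In section 4, keep chi-square as the unadjusted, descriptive display. For comparisons of ORR and DCR, name multivariable logistic regression as the main analysis, with the same baseline covariates as the Cox models and with adjustment or stratification by line of therapy. For grade 3 or higher adverse events, report crude proportions and, where treatment start and stop dates are available, add exposure-adjusted rates as a supplementary comparison.

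For ORR and DCR the cost is a sentence or two and a few model fits. Section 4 already lists histology, sites of metastases, BMI, concomitant medication, laboratory tests and treatments for collection. Sparse event counts will limit the number of covariates in smaller groups. For adverse events the cost is less certain. Section 4 does not list treatment stop dates or event onset dates, so their availability must be confirmed first, and the supplementary analysis should not be promised for centres that cannot supply them.

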3.1 Inclusion Criteria

- Patients aged $>18y$
- Histologically confirmed diagnosis of UC of upper and/or lower urinary tract
- Histologically or radiologically confirmed metastatic disease
- Treatment with pembrolizumab in patients progressed after previous platinum-based chemotherapy
- Treatment with pembrolizumab as a first-line therapy in the platinum-unfit patients
- Treatment with enfortumab vedotin in patients progressed to previous platinum-based chemotherapy and anti-PD-1/PD-L1 inhibitor.

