Clinical data retrospectively extracted from paper and electronic charts will be collected in Excel datasets. The data will be anonymized and a code will be used for each individual patient included in the study. For each patient, the following data will be collected in the database of each participating institution: histology, surgery, sites of metastases, Body Mass Index (BMI), concomitant medication, radiotherapy, laboratory tests and treatments. Patients without sufficient data on follow-up and response to therapy will be excluded from this study.

5. End-dates for Data Collection and Publication

Due to the large number of Centers involved from different Countries, we have scheduled a series of deadlines in order to complete step-by-step the planned analyses and prepare the manuscripts for publication:

- The first deadline is July 1st, 2024 - analysis of data collection and preparation of four of our planned manuscripts within 31th August, 2024
- The second deadline is September 1st, 2024 - analysis of data collection and preparation of the other planned manuscripts within October 31th, 2024

For each manuscript, one author's name for each Institution involved in this project will be considered. We will consider, according to Journal policies, two names for each Oncological Center that has enrolled at least 50 patients in the dataset or which has substantially participated to the different phases of the manuscripts.

Before the submission, a draft of each manuscript will be sent to all the authors from the Institutions involved in order to revise potential errors and propose additional comments and suggestions.

Potential publication fees will be sustained by the Center of the Principal Investigator (Macerata Hospital).

6. Data Confidentiality and Management

Information about study subjects will be kept confidential and managed under the

The ARON PROJECT

Global experiences, perspectives and access to cure in patients with genitourinary tumors

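### The protocol does not define which eligible charts enter this retrospective cohort, and its data-sufficiency and consent rules can make entry depend on survival

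*Protocol*

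**What the plan says.** Section 2 describes an "International Multicentric Retrospective Study to collect global experiences with the use of pembrolizumab and enfortumab vedotin". Section 4 gives the source: "Clinical data retrospectively extracted from paper and electronic charts will be collected in Excel datasets".

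Section 3.1 selects on age, histology, metastatic disease and treatment setting. The treatment criteria read, for example, "Treatment with pembrolizumab in patients progressed after previous platinum-based chemotherapy" and "Treatment with enfortumab vedotin in patients progressed to previous platinum-based chemotherapy and anti-PD-1/PD-L1 inhibitor". Section 3.2 excludes only patients without confirmed histology or confirmed metastatic disease. Neither section gives treatment-start dates, asks for all or consecutive eligible patients, or asks for a list of those not entered.

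The other relevant provisions are these:

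- **Section 4:** "Patients without sufficient data on follow-up and response to therapy will be excluded from this study". No threshold for sufficiency is given.
- **Section 2.3:** for PFS, patients lost to follow-up are censored.
- **Section 8:** written consent is needed before a patient may be included. No provision is stated for patients who have died.
- **Section 5:** the only calendar dates are the 2024 data-collection and manuscript deadlines. The authorship rule allows "two names for each Oncological Center that has enrolled at least 50 patients in the dataset". A centre that contributes substantially to the manuscripts can qualify by that route instead.
- **Section 6:** the Principal Investigator answers for the completeness of the data entered. That covers entered records, not eligible patients who were never entered.

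**The concern.** Real-world efficacy is the primary end-point (Section 2.1). An estimate of real-world survival describes treated patients only if the entered patients represent those treated. Here charts are read after the event, and the protocol does not say how eligible charts become study patients.

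Two written rules can also tie entry to survival. A patient who dies before the first response scan has no scan-based response. Section 4 can be read as removing that patient from OS as well as from ORR. A patient who has died cannot sign a new consent form, so Section 8 read literally could keep out deaths that occurred before data collection.

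If either rule works this way, OS, PFS and ORR would look better than they are. Without a count of eligible patients, a reader could not tell how far.

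**Working it through.** **Step 1: search for a sampling frame.** The whole protocol was read for a treatment-start window, an all-eligible or consecutive rule, a screening log and central chart selection. None is present. The 12-month figure in Section 3.3 ("for a minimal observation time of 12 months") is an input to the pembrolizumab sample size, not an entry rule.

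**Step 2: Sections 4 and 2.3 side by side.** Section 2.3 keeps patients lost to follow-up in PFS as censored. Section 4 removes patients with insufficient follow-up and response data from the study. With no threshold, the same patient could be censored at one centre and excluded at another.

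**Step 3: sensitivity of 12-month OS (enfortumab vedotin).** Inputs from Section 3.3 are the registration-study 12-month OS of 51.5% (95% CI 44.6 to 58.0), the hypothesised 60%, and 311 evaluable patients. The assumed quantity is f, the share of patients dead by 12 months who are not entered. All survivors are taken to be entered.

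Observed OS = p / (1 − f(1 − p)), with p = 0.515:

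- f = 0.10: 0.515 / (1 − 0.0485) = 54.1%
- f = 0.20: 0.515 / (1 − 0.0970) = 57.0%
- f = 0.292: 0.515 / (1 − 0.1416) = 60.0%

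The f that turns p into 60% is f = 1 − 0.4p / (0.6(1 − p)):

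- p = 0.515: 1 − 0.2060/0.2910 = 29%
- p = 0.446: 1 − 0.1784/0.3324 = 46%
- p = 0.580: 1 − 0.2320/0.2520 = 8%

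**Step 4: effect on a test.** Section 3.3 names no null value, so 51.5% is assumed, with a two-sided 0.05 one-sample test at n = 311. The upper critical value is 0.515 + 1.96 × √(0.515 × 0.485/311) = 0.5706. With true OS at 51.5%, the chance of exceeding it is 2.5% at f = 0, 15% at f = 0.10, 50% at f = 0.20 and about 86% at f = 0.292.

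**Step 5: bounds from the plan's own attrition.** The plan includes 361 patients and needs 311 evaluable, a loss of 50. 50/361 = 13.9%, inside the stated 10–15%. At 51.5%, 361 patients give 185.9 alive and 175.1 dead at 12 months.

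- All 50 lost are deaths: 185.9/311 = 59.8%
- All 50 lost are survivors: 135.9/311 = 43.7%

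These are extremes, not forecasts. They show that the direction is open.

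**Step 6: pembrolizumab, for scale.** Section 3.3 gives a control median of 7.4 months and a hazard ratio of 0.73. Assuming exponential survival, the median is 7.4/0.73 = 10.14 months and 12-month OS is 0.5^(12/10.14) = 44.0%. Then f = 0.10 gives 0.440/(1 − 0.056) = 46.6%, and f = 0.20 gives 0.440/(1 − 0.112) = 49.6%.

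**The case against.** The case against has real force on several points.

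- **Centre choice.** A reader might infer that centres pick the charts they like. No section says so, and Section 3 speaks simply of patients treated with the drugs. The text supports only that the selection method is not stated.
- **Authorship.** A reader might infer that the 50-patient rule encourages selection of good outcomes. It rewards volume, offers substantial participation as another route, and is subject to journal policy. A centre below 50 gains by entering every eligible patient, early deaths included. The rule is not evidence of outcome-based selection.
- **Recent starters.** A reader might infer that patients treated shortly before the July 2024 deadline bias OS because 12 months of observation is not enforced. Kaplan-Meier estimation handles them by censoring. Their effect is fewer events, which is a matter of precision.
- **Direction.** The Section 4 exclusion could also remove living patients with poor follow-up, so upward bias is possible but not shown.
- **Irreparability.** It would be too strong to say that no analysis can reveal or address the problem. Between-centre comparison may signal it, and a tipping-point calculation such as Step 3 can bound it.

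What remains is the absence of a sampling frame, together with two rules that can act on survival. Who enters the cohort is a protocol matter and not a detail normally left to a SAP.

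**Conclusion.** The concern holds as a gap in design. The protocol leaves the sampling frame undefined, and Sections 4 and 8 as written permit survival-dependent entry. Analysis can bound the effect of patients never entered but cannot recover them.

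The direction and size of any bias are unknown. Modest selective omission would matter: leaving out 10% of 12-month deaths moves 51.5% to 54.1%, and about 29% would show the hypothesised 60% with no real gain. Nothing in the protocol indicates what the omission rate would be. The figures also assume that every survivor is entered and that the registration rate applies to this population.

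**What to change.** In Section 3:

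- State the first and last treatment-start dates for each drug.
- Require each centre to enter all consecutive eligible patients who started within that window.
- Report per centre the number eligible, entered and not entered, with reasons.

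In Section 4, limit the exclusion for insufficient data to the response analysis and report how many patients it removes. Keep patients without a response assessment in OS and PFS, censored at last contact if event-free. This also brings Section 4 into line with Section 2.3.

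In Section 8, reconcile the consent requirement with the inclusion of deceased patients, as the ethics committees and local rules allow. Without this, a consecutive-entry rule could still leave deaths out.

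The authorship rule need not change, and patients who started within 12 months of the data cut need not be excluded. The cost is protocol wording and some extra listing work at each centre, for example from pharmacy or clinic lists.
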